3.1.3 Change from baseline

Absolute change from baseline outcome variables are computed as:

$$(post-baseline value - baseline value).$$

Percent change from baseline outcome variables are computed as:

$$((post-baseline value - baseline value) / (baseline value)) *100$$

If either the post-baseline value or the baseline value is missing, then both change from baseline and percent change from baseline value will also be set to missing. If the baseline value is zero, the percent change will be set to missing.

3.1.4 Visit windows

For efficacy endpoints that present visit-based data, variables will be summarized based on the scheduled days with adjusted analysis-defined visit windows. The adjusted analysis-defined windows will be based on the collection schedule as per the CSP Table 2 and variables will be windowed to the closest scheduled visit for that variable.

Visit windows following baseline will be constructed in such a way that the upper limit of the interval falls half way between two visits (the lower limit of the first post-baseline visit will be Study Day 2). If an even number of days exists between two consecutive visits, then the upper limit will be taken as the midpoint value minus 1 day. Visit windows are constructed so that every observation collected can be allocated to a particular visit. No visit windows will be defined for screening visits.

For assignment of data to adjusted analysis-defined visit windows, study day will be defined as follows:

$$(Date of assessment - date of randomization) +1$$

By this definition, the day of randomization will be Study Day 1 and the planned date of Visit 4 (Week 4) will be Study Day 29 (=28+1), for example.

The adjusted analysis-defined windows for assessments conducted during the double-blind period at every visit from Visit 3 to Visit 13 are summarized in Table 2.

Table 2 Visit windows for assessments conducted at every visit from Visit 3 to Visit 13 – Double-blind treatment period

Adjusted defined window visit*	Scheduled study day	Maximum windows
Week 2	15	$2 \leq \text{Study day} \leq 21$
Week 4	29	$22 \leq \text{Study day} \leq 35$
Week 6	43	$36 \leq \text{Study day} \leq 49$
Week 8	57	$50 \leq \text{Study day} \leq 70$
Week 12	85	$71 \leq \text{Study day} \leq 98$
Week 16	113	$99 \leq \text{Study day} \leq 126$
Week 20	141	$127 \leq \text{Study day} \leq 154$
Week 24	169	$155 \leq \text{Study day} \leq 182$
Week 28	197	$183 \leq \text{Study day} \leq 210$
Week 32	225	$211 \leq \text{Study day} \leq 237$
Week 36	253	$238 \leq \text{Study day} \leq \text{Visit 13 study day or 280 whatever is earlier}$

*All data are re-windowed apart from any baseline data. This is to account for any delayed IP during Visit 2 (Week 0) to still be assessed as baseline.

The adjusted analysis-defined windows for assessments conducted during the OLE period at every visit from Visit 14 are summarized in Table 3.

Table 3 Visit windows for assessments conducted at every from Visit 14 – OLE

Adjusted defined window visit*	Scheduled study day	Maximum windows
Week 40	281	Visit 13 date or 280 whatever is earlier < Study day \leq 295
Week 44	309	$296 \leq$ Study day \leq 323
Week 48	337	$324 \leq$ Study day \leq 351
Week 52	365	$352 \leq$ Study day \leq 379
Week 56	393	$380 \leq$ Study day \leq 407
Week 60	421	$408 \leq$ Study day \leq 435
Week 64	449	$436 \leq$ Study day \leq 463
Week 68	477	$464 \leq$ Study day \leq 491
Week 72	505	$492 \leq$ Study day \leq 519
Week 76	533	$520 \leq$ Study day \leq 575
Week 88	617	$576 \leq$ Study day \leq 659
Week 100	701	$660 \leq$ Study day \leq 743
Every 12 weeks	Scheduled Study Day	$744 \leq$ Study day \leq Scheduled Study Day + 42

If multiple assessments are recorded within a single adjusted visit window, please refer to the rules below.

If there are 2 or more observations within the same visit window, then the non-missing observation closest to the scheduled study day will be used in the analysis.

If 2 observations are equidistant from the scheduled study day, then the non-missing observation with the earlier collection date will be used in the analysis.

If 2 observations are collected on the same day then the non-missing observation with the earlier collection time will be included in the analysis.

If two or more values are located on the same side of the target day at the same date and time and are the closest to the target day, the mean of the values will be included in the analysis.

Note: in summaries of extreme values all on-treatment post baseline values collected are used including those collected at unscheduled visits regardless of whether the value is closest to the target visit day.

If a visit window does not contain any observations, then the data will remain missing.

For endpoints which are not collected at every visit, the above rules will be applied to derive adjusted analysis-defined visit windows based on the protocol defined visit schedule for that endpoint. Similarly, for laboratory parameters not collected at every visit.

When converting the number of days to other units, the following conversion factors will be used: 1 week = 7 days; 1 year = 365.25 days.

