The primary endpoint is the proportion of participants who are in complete remission while off OCS for ≥ 2 months at Week 36.

A participant will be considered in complete remission for ≥ 2 months at Week 36 if a complete remission is recorded in the disease status eCRF at the clinical assessment which is assigned to the Week 36 visit when applying the windowing rules described previously, and a complete remission is recorded at least 55 days prior to this Week 36 date, and all evaluable disease states that are recorded during the 55 days between these assessments (ie, overall 8 weeks) are complete remission.

The disease state at each visit will be recorded on the eCRF form collecting the date of assessment and the disease state. A disease state clinical assessment reported in the eCRF as “Not Evaluable” will be considered as missing. Between two consecutive non-missing disease state assessments it will be assumed that the disease state collected at the first assessment is

current until the day before the second disease state assessment, unless intercurrent events happen. The same rule will be applied for two non-consecutive non-missing disease state assessments at windowed visits if at least one missing assessment is detected between them.

A participant will be considered off OCS for ≥ 2 months at Week 36 if off OCS on the day of the clinical assessment which is assigned to the Week 36 visit when applying the windowing rules and on the 55 days (ie, overall 8 weeks) before that date. Further details on the definition of day off OCS are contained in Section [3.1.5.1](#).

A participant will be considered in complete remission while off OCS for ≥ 2 months at Week 36 if both the definitions above are met.

Note that regardless of prior OCS use, participants who have been in complete remission while off OCS for ≥ 2 months at Week 36 will be classed as responders. For example, if participants require an increase in OCS dose after previously achieving disease control but they still taper and achieve the remission criteria by Week 36, this will be counted as response in the analysis. It is considered unlikely that this situation would emerge often, but given the clinical relevance of still being able to achieve remission and that OCS use is built into the remission definition, it is considered appropriate to count this situation as response in the analysis.

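### SAP Table 2 starts the Week 36 window one day early: by the SAP's own rule Day 238 belongs to Week 32, although the effect on results is probably nil

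*SAP*

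**What the plan says.** SAP 3.1.4 gives a principle, a construction rule and a table.

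- **Principle:** "variables will be windowed to the closest scheduled visit for that variable".
- **Rule:** "Visit windows following baseline will be constructed in such a way that the upper limit of the interval falls half way between two visits". For even gaps: "If an even number of days exists between two consecutive visits, then the upper limit will be taken as the midpoint value minus 1 day".
- **Study-day convention:** randomization is Day 1, and "the planned date of Visit 4 (Week 4) will be Study Day 29 (=28+1), for example". Scheduled days are therefore 7 × week + 1.
- **Table 2:** the Week 32 window runs from Day 211 to Day 237. The Week 36 window runs from Day 238 to the earlier of the Visit 13 day and Day 280.
- **Several records in one window:** the non-missing one nearest the scheduled day is used.

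SAP 3.2 relies on these windows. One condition for response is that "complete remission is recorded in the disease status eCRF at the clinical assessment which is assigned to the Week 36 visit", and both the remission and the off-OCS look-backs of 55 days are counted from that date. Assessments from scheduled, unscheduled, discontinuation, end-of-treatment and follow-up visits can all fill the window. If Week 36 is missing, the participant is a non-responder on the primary endpoint (SAP 3.2) or is multiply imputed for BPDAI activity and pruritus (SAP 3.3.3 and 3.3.4). SAP Section 6, which lists departures from the protocol, mentions no special treatment of this boundary.

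**The concern.** The Week 32/Week 36 boundary is the one that feeds the primary endpoint, and it is the only boundary between two double-blind visits that does not follow the written rule. Someone who programs from the rule and someone who programs from the table would assign a Day 238 record to different visits, and the SAP does not say which source governs.

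At stake is a participant whose last usable assessment falls on Day 238. Under Table 2 that record is an observed Week 36 result. Under the rule it belongs to Week 32, and Week 36 is missing. On the primary endpoint that can separate a responder from a non-responder; for BPDAI and pruritus it separates an observed value from an imputed one.

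**Working it through.** **Inputs.** Scheduled days and printed limits come from SAP 3.1.4, Tables 2 and 3. Visit windows of ±3 days come from the protocol's Schedule of Activities. The 50 participants per arm come from SAP 1.3.

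**Formula.** With consecutive scheduled days d1 and d2, midpoint = (d1 + d2)/2. If d2 − d1 is even, upper limit = midpoint − 1.

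**Step 1: reproduce Table 2.**

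| Window | d1 | d2 | Gap | Midpoint | Rule | Table 2 |
|---|---|---|---|---|---|---|
| Week 2 | 15 | 29 | 14 | 22 | 21 | 21 |
| Week 4 | 29 | 43 | 14 | 36 | 35 | 35 |
| Week 6 | 43 | 57 | 14 | 50 | 49 | 49 |
| Week 8 | 57 | 85 | 28 | 71 | 70 | 70 |
| Week 12 | 85 | 113 | 28 | 99 | 98 | 98 |
| Week 16 | 113 | 141 | 28 | 127 | 126 | 126 |
| Week 20 | 141 | 169 | 28 | 155 | 154 | 154 |
| Week 24 | 169 | 197 | 28 | 183 | 182 | 182 |
| Week 28 | 197 | 225 | 28 | 211 | 210 | 210 |
| Week 32 | 225 | 253 | 28 | 239 | **238** | **237** |

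Nine of ten agree. Week 32 has the same 28-day gap as the five rows above it and is one day short.

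**Step 2: try the other reading.** If the even-number clause counts days strictly between visits, the count is 27 (odd), the subtraction does not apply, and Week 32 ends at 239. The other nine rows would then all be wrong. Neither reading gives 237.

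**Step 3: check the nearest-visit principle.**

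| Day | From Week 32 (225) | To Week 36 (253) |
|---|---|---|
| 237 | 12 | 16 |
| 238 | 13 | 15 |
| 239 | 14 | 14 |

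Day 238 is nearer to Week 32. Day 239 is the tie.

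**Step 4: who can have a Day 238 record?** On-schedule visits cannot: Visit 12 spans Days 222–228 (225 ± 3) and Visit 13 spans Days 250–256 (253 ± 3). A discontinuation visit 4 weeks ± 7 days after the last dose falls on about Days 215–235 after an on-time Week 28 dose (197 + 28, ± 7 ± 3) and Days 243–263 after a Week 32 dose (225 + 28, ± 7 ± 3). The 12-week follow-up visit gives the same ranges after Week 20 (141 + 84) and Week 24 (169 + 84) doses. What remains is an unscheduled visit, an off-window visit, or a discontinuation visit held early, which a Schedule of Activities footnote allows.

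**Step 5: size.** One reclassified participant in an arm of 50 is 1/50 = 2 percentage points.

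**Step 6: Table 3.** Its twelve fixed upper limits equal the midpoint itself. For example, (281 + 309)/2 = 295 and (617 + 701)/2 = 659; the Week 100 limit, (701 + 785)/2 = 743, takes Week 112 as the next visit. The 12-weekly row keeps 744 as the lower limit throughout. Read literally, Week 112 (Day 785) runs from 744 to 827 and Week 124 (Day 869) from 744 to 911, so they overlap.

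**The case against.** The strongest reply is that the slip has almost no route into the results.

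- **Displacement.** A reader might infer that any Day 238 assessment is analysed as Week 36. It is not. SAP 3.1.4 takes the non-missing record nearest Day 253, so an on-time Visit 13, or any non-missing assessment from Day 239 up to it, displaces Day 238. This objection stands.
- **Withdrawals.** A reader might infer that participants who withdraw after Day 238 become responders. Protocol 9.4.2.1 and SAP Appendix 8.1.2 treat withdrawal before Week 36 as non-response, which covers most participants without a Visit 13. This largely stands. Some ambiguity remains, because SAP 3.2 starts the non-response only after the last available disease-state assessment, which here would be the Day 238 record itself.
- **The correction leaves early records in place.** From Day 239, 14 days before target, an early assessment can still stand in for Week 36. That is true; the correction aligns the table with its rule and does no more.
- **The Week 36 upper limit.** Midpoint minus 1 against Week 40 would be (253 + 281)/2 − 1 = 266, not Day 280. A reader might call this a second error, but it works as a cut-off for the double-blind period, not as a midpoint.
- **Table 3.** A reader might infer that the OLE limits are wrong. They match the text if only days strictly between visits are counted, so the documents show two conventions in use, not a clear error. The nearest-visit principle can also resolve the overlapping 12-weekly windows. The OLE analyses are descriptive without hypothesis tests (SAP 4.1), and the visible OLE endpoints stop at Week 72 (SAP 3.6.9).

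None of this supplies a reading under which Week 32 ends at Day 237.

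**Conclusion.** The Table 2 boundary is wrong by one day under the SAP's rule as applied in every earlier row, and under its nearest-visit principle. Day 238 belongs to Week 32.

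The consequence is narrow. A primary result changes only if a participant was assessed on Day 238, has no non-missing assessment in the window nearer to Day 253, is not already a non-responder through withdrawal or restricted medication, and meets the complete-remission and off-OCS conditions over the 55-day look-back. For BPDAI, pruritus and IGA the first two conditions are again needed. The expected number affected is probably zero and at most about one. That is a judgement from the visit schedule, since the documents give no distribution of visit days, and the 2-point shift is a worst case. Sample size, power and alpha do not depend on this boundary.

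The Table 3 difference is a matter of consistency, and no inference rests on it.

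**What to change.** Before unblinding, change Table 2 in SAP 3.1.4 to Week 32: Days 211 to 238, and Week 36: Day 239 to the earlier of the Visit 13 day and Day 280. Add a note that this last limit is a period cut-off and not a midpoint. If 237 was intended, state the reason instead.

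For consistency, state one midpoint convention and use it in both tables. If it is midpoint minus 1, the Table 3 limits become 294, 322, 350 and so on, and the 12-weekly upper limit becomes the scheduled day plus 41. In either case, start each 12-weekly window one day after the previous window's upper limit.

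The cost is a few table entries and a matching check of the windowing program. Doing it before unblinding means the boundary is not settled with results in view.

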3.1.5 Prior/concomitant medications

Medications will be categorized according to the WHO Drug Reference List dictionary which employs the Anatomical Therapeutic Chemical (ATC) classification system. The most recent version that will have been released for execution at AstraZeneca/designee per the Data Management Plan will be used.

A medication will be regarded as prior if it was stopped on or before the date of randomization (medication stop date \leq date of randomization). A medication will be regarded as ‘concomitant’ if the start date is on or after the date of randomization or if it started prior to the date of randomization and was ongoing after the date of randomization. If a medication was started and stopped on the date of randomization, it will be considered as concomitant.

No medication data will be imputed unless differently stated. The handling of partial/missing dates for prior/concomitant medications is detailed in Appendix [8.3](#). Duration of prior/concomitant medications will not be calculated using imputed dates and will instead be set to missing unless differently stated.

3.1.5.1 OCS usage

During the double-blind period, participants will be treated with IP and OCS until BP disease control is achieved (Figure [1](#)), as detailed in the CSP Section 6.5.

During the OLE period, participants can receive corticosteroids (topical and/or oral) for BP relapse at the Investigator’s discretion, with the goal of tapering off the steroids to benralizumab monotherapy as soon as clinically indicated.

The participants will be asked to report daily the dosage of OCS taken over the past 24 hours on a provisioned handheld device at home. Details about OCS usage will then be collected at each scheduled visit by the Investigator. Only data collected in the electronic case report form (eCRF) will be included in the main OCS analysis.

A participant will be considered on OCS on a date if that date is included in the interval

OCS start date \leq date \leq OCS end date

Only OCS collected in the OCS eCRF form with dose > 0 will be considered. For any of the OCS with missing dose, the dose will be assumed to be the same of the latest of the previous OCS doses with dose > 0 . If end date is missing the OCS will be considered ongoing and the participant assumed to be on OCS until last contact for the participant.

Partial/missing dates for OCS during the study (apart from end date for ongoing OCS) are not allowed.

Any increase in OCS dose after BP disease control is achieved will be considered as OCS rescue use.

3.1.5.2 Restricted medications

Restricted medications are detailed in the CSP Section 6.5.2 and will be selected considering a list of ATC codes that will be agreed and documented before unblinding (for the double-blind period) and final DBL (for the OLE period).

Only certain types of restricted medications used after randomisation during the double-blind period will be considered intercurrent events in the analyses, and only these cases will be handled as described in the estimand approaches detailed in Sections [4.2.6.1](#) and [4.2.6.2](#).

The restricted medications that will be considered intercurrent events include the following treatments if given to treat the participants BP, or if given for another condition but where prolonged use is deemed likely to substantially affect their BP outcomes:

- Immunosuppressive medications
- Anti-microbial agents with anti-inflammatory properties (eg. Tetracycline antibiotics, dapsone, erythromycin) – these are specific examples only, but review prior to unblinding will confirm if any others should be considered
- Topical corticosteroids
- Any marketed or investigational biologic (monoclonal or polyclonal antibody)
- Other IPs during the study or within 12 weeks after the last dose of benralizumab/placebo

In addition, for the endpoints where an increase in OCS use post disease control is considered an intercurrent event with consequence, this will only be in the case of OCS use with the aim of treating the participants BP, in a similar approach to the restricted medications described above. Short bursts of OCS use for other conditions (eg. COPD/asthma exacerbation) will not automatically trigger the estimand approach described.

A full review on concomitant medications will be performed prior to unblinding and the final list of intercurrent events will be confirmed and documented then.

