Participants who are treated with OCS and then tapered can be at risk for acute adrenal insufficiency. The possibility of acute adrenal insufficiency should be considered, according to the guidance in [Appendix G](#), in any acutely unwell participant undergoing withdrawal of chronic systemic corticosteroid treatment. Assessment of hypothalamic-pituitary-adrenal axis integrity may be performed, according to standard of care, at the discretion of the Investigator.

If the Investigator is considering addition of an immunosuppressant for the treatment of BP relapse, a discussion with the designated study physician should occur to review study options which may include discontinuation of IP. If in the opinion of the Investigator, a participant requires the addition of immunosuppressants for control of relapse, the participant will discontinue IP administration. Participants who are in the double-blind period will be asked to complete all visits and study assessments up to Week 36. Participants who are in the OLE will withdraw from the study and will be asked to complete the study assessments for the final follow-up visit as outlined in the SoA ([Table 2](#)).

While OCS compliance will be captured daily on the handheld device (unless exempted), the main source of data for analysis of OCS-related endpoints will be saved in the eCRF.

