Intercurrent events for this estimand are unfavorable outcomes and will be handled with a composite strategy. The set of intercurrent events consists of participants who receive medications deemed to be intercurrent events as per Section [3.1.5.2](#) and participants who withdraw from the study. The primary estimand will regard these participants as non-responders from the time such events occur up to Week 36.

Participants who withdraw from the study will be considered non-responders starting after the last available non-missing BP disease state clinical assessment.

Participants who receive medications deemed to be intercurrent events as per Section [3.1.5.2](#) will be considered non-responders starting from the date of start of restricted medications. Missing/partial start dates are not allowed for restricted medications.

Participants with missing data at Week 36 for any other reason will be considered as non-responders.

The amount of missing data for this study is expected to be low, as participants who prematurely discontinue IP will be asked to come in for all visits and complete all study assessments up to the end of the study.

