3.4 Secondary efficacy outcome variables

3.4.1 Proportion of participants in sustained complete/partial remission on minimal OCS/off OCS for at least 2 months at Week 36

A supportive responder analysis will be performed where any participants who achieve complete or partial remission while on minimal OCS or off OCS for at least 2 months at Week 36 will be defined as responders.

The same derivation rules and the same intercurrent events described for the primary analysis will be applied.

3.4.2 Cumulative time (weeks) in complete remission off OCS from baseline to Week 36

Cumulative time in complete remission while off OCS will be derived for each participant over the initial 36-week treatment period.

Cumulative time in complete remission while off OCS will be computed summing the days included in all the time intervals between each remission and the following relapse according to the below rules.

If there is no OCS usage from and inclusive of the date when complete remission is assessed until the day before the date of relapse, then cumulative time in complete remission while off OCS will be computed in weeks as:

$$(date\ of\ relapse - date\ of\ complete\ remission) / 7$$

If there is OCS usage on the date of complete remission and the complete remission is confirmed at a later assessment after the OCS usage stop date, then cumulative time in complete remission while off OCS will be computed in weeks as:

$$(date\ of\ relapse - first\ day\ off\ OCS\ after\ remission\ and\ before\ relapse) / 7$$

If the OCS usage stop date is after the last assessment of complete remission then the time will be imputed as equal to zero.

If there is OCS usage after complete remission off OCS that is before or on the day prior to the date of relapse then, the cumulative time in complete remission while off OCS will be computed in weeks as:

$$(last\ day\ off\ OCS\ after\ remission\ and\ before\ OCS\ restart - date\ of\ complete\ remission + 1) / 7$$

For participants who do not have a relapse after a complete remission, the time interval from the complete remission until the date of the BP disease state allocated to Week 36 will be considered for computing the cumulative time in the interval.

For more details about definition of days on or off OCS see Section [3.1.5.1](#).

These times will then be assigned to a set of ordered categories:

- Category Value = 0 for cumulative time = 0 days
- Category Value = 1 for $0 < \text{cumulative time} \leq 56$ days (8 weeks)

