- Category Value = 2 for $56 \text{ days (8 weeks)} < \text{cumulative time} \leq 112$ days (16 weeks)
- Category Value = 3 for $112 \text{ days (16 weeks)} < \text{cumulative time} \leq 168$ days (24 weeks)
- Category Value = 4 for cumulative time > 168 days (24 weeks)

Depending on the distribution of the data, categories might be condensed or expanded. Any such decisions will be documented prior to unblinding.

The set of intercurrent events for this estimand consists of participants who receive medications deemed to be intercurrent events as per Section [3.1.5.2](#) and participants who withdraw from the study.

Participants who receive medications deemed to be intercurrent events as per Section [3.1.5.2](#) will be considered with a relapse on the date of start of restricted medications. For restricted medications during the study missing/partial start dates are not allowed.

Participants who withdraw from the study will be considered with a relapse starting after the last available BP disease state clinical assessment.

Note that the list of intercurrent events does not include increases in OCS dose after achieving disease control, and all doses of OCS will be included in the derivation of cumulative time in complete remission while off OCS.

3.4.2.1 Cumulative time (weeks) in complete or partial remission off OCS from baseline to Week 36

Cumulative time (weeks) in complete or partial remission off OCS from baseline to Week 36 will be also computed, as additional endpoint analysed in an exploratory way.

Derivation rules and intercurrent events described in Section [3.4.2](#) for the cumulative time in complete remission while off OCS will be applied.

3.4.3 Proportion of participants off OCS by Week 36

Participants will be defined as responders if they are off OCS by Week 36. Otherwise, participants will be classified as non-responders.

A participant will be considered off OCS at Week 36 if the participant is off OCS prior to the date of the BP disease state allocated to Week 36. Further details on the definition of days off OCS are contained in Section [3.1.5.1](#).

The set of intercurrent events for this estimand consists of participants who receive medications deemed to be intercurrent events as per Section [3.1.5.2](#) and participants who withdraw from the study. The primary estimand will regard these participants as non-responders from the time such events occur up to Week 36.

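### Cumulative time in remission off OCS (SAP 3.4.2) still counts remission first recorded after an intercurrent restricted medication has started

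*SAP*

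**What the plan says.** SAP 3.1.5.2 lists the drug classes that become intercurrent events: "The restricted medications that will be considered intercurrent events include the following treatments if given to treat the participants BP", or if given for something else where long use is likely to change BP outcomes. For handling, it points to SAP 4.2.6.1 and 4.2.6.2, which cover the primary analysis and its subgroups.

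SAP 3.4.2 has its own rule for cumulative time in complete remission off OCS. The endpoint is built by "summing the days included in all the time intervals between each remission and the following relapse". Where no relapse follows, "the time interval from the complete remission until the date of the BP disease state allocated to Week 36 will be considered". A participant who takes an intercurrent medication "will be considered with a relapse on the date of start of restricted medications". Nothing further is said about the time after that date. SAP 3.4.2.1 (complete or partial remission) takes over the same rules.

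For the primary endpoint, SAP 3.2 treats the same event differently: "The primary estimand will regard these participants as non-responders from the time such events occur up to Week 36". SAP 3.4.3 (off OCS by Week 36) uses that rule too.

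Data continue to be collected after the event. When an immunosuppressant is added and IP is stopped, Protocol 6.5.1 states: "Participants who are in the double-blind period will be asked to complete all visits and study assessments up to Week 36".

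**The concern.** A relapse dated on one day can only close a remission interval that is open on that day. The endpoint allows re-entry, so a remission recorded later opens a new interval, and nothing in SAP 3.4.2 stops it from counting. A participant who is a failure on the primary endpoint because a restricted drug was needed can therefore build up remission time on this endpoint while taking that drug.

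The same relapse sentence appears in SAP 3.3.1 for time to first relapse. It works there because the first relapse ends the outcome. It does not work the same way when intervals are summed.

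At stake is what the endpoint measures. SAP 3.3.2 rejects a treatment-policy approach for OCS exposure because restricted drugs would confound later OCS use. Time off OCS is open to the same confounding, yet SAP 3.4.2 comes close to a treatment-policy result while naming the drug an intercurrent event.

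**Working it through.** The plan gives no sample size, power or expected value for this endpoint (SAP 1.3 concerns the primary endpoint only), so there is no planned figure to reproduce. The check applies the SAP 3.4.2 rules to hypothetical histories.

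**Inputs**
- Study days: randomization is Day 1 (SAP 3.1.4), so Week w is Day 7w + 1. Week 20 = Day 141, Week 24 = Day 169, Week 28 = Day 197, Week 36 = Day 253.
- Closed interval: relapse date minus remission date. Open interval: Week 36 assessment date minus remission date.
- Categories: 0 for 0 days; 1 up to 56; 2 up to 112; 3 up to 168; 4 above 168.
- Assumptions: off OCS throughout the counted remission; after a deemed relapse, remission resumes at the next assessment that records it, in line with the carry-forward convention in SAP 3.2.

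**Case 1: no interval open when the drug starts.** Drug from Day 99 (Week 14), active disease until then, complete remission off OCS from Day 169 to Day 253.
- The deemed relapse on Day 99 closes nothing, so it removes 0 days.
- The later interval is 253 − 169 = 84 days (12 weeks). Since 56 < 84 ≤ 112, this is category 2.
- With failure held up to Week 36, the result is 0 days, category 0.
- On the primary endpoint, remission off OCS recorded 84 days before Week 36 exceeds the required 55 days. The intercurrent-event rule alone makes this participant a non-responder.

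Further histories, with the drug started the day after the first visit shown and active disease before remission:

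| Drug starts after | Remission from | Days as written | Category | If failure held to Week 36 |
|---|---|---|---|---|
| Week 8 | Week 12 (Day 85) | 253 − 85 = 168 | 3 | 0 days, category 0 |
| Week 12 | Week 20 (Day 141) | 253 − 141 = 112 | 2 | 0 days, category 0 |
| Week 16 | Week 24 (Day 169) | 253 − 169 = 84 | 2 | 0 days, category 0 |
| Week 24 | Week 28 (Day 197) | 253 − 197 = 56 | 1 | 0 days, category 0 |

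**Case 2: an interval is open.** Remission off OCS from Day 141, drug from Day 170, remission recorded again on Day 197 and through Day 253.
- As written: (170 − 141) + (253 − 197) = 29 + 56 = 85 days, category 2.
- With failure held up to Week 36: 29 days, category 1.
- With no drug: 253 − 141 = 112 days, category 2.
- The deemed relapse removes 112 − 85 = 27 days, which is the gap 197 − 170 to the next assessment.

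**The case against.** The strongest reply is that the SAP sets intercurrent-event handling endpoint by endpoint: non-responder in 3.2, data dropped after the event in 3.3.2, last value carried forward in 3.3.3. A cumulative-time measure that allows re-entry may reasonably differ from a single-timepoint responder, so a difference from the primary endpoint is not in itself an error. That is right as a principle. However, SAP 3.4.2 does not say that remission on the drug is meant to count, SAP Section 6 does not list it as a choice, and the protocol leaves non-key estimands to the SAP. An event named as intercurrent that removes no days in Case 1 needs either a consequence or a stated reason for having none.

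The second reply concerns size. SAP 4.2.7.2 expects relapses to be treated with OCS and restricted medications to be infrequent. Crediting also requires complete remission and being off OCS, both before Week 36. This stands and limits the likely effect.

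Three stronger readings are tempting but unsupported:
- That the rule does nothing at all. Case 2 shows that it closes an open interval and removes some days.
- That most such drugs start before any remission. The documents give no frequency, and a participant who remitted, relapsed and then received the drug keeps the earlier interval either way.
- That the loss can be expressed as a particular odds ratio. Borrowing the 50% and 20% of SAP 1.3 would use primary-endpoint rates, add invented percentages of credited participants, and reduce a five-category model to any time versus none.

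**Conclusion.** The concern holds. Read literally, SAP 3.4.2 counts complete remission first recorded after an intercurrent medication starts, on all days also off OCS. In the Day 99 example this is 84 days (category 2) instead of 0 (category 0), for a participant who fails both the primary endpoint and the off-OCS endpoint up to Week 36. Where remission is already open, only the gap to the next assessment recording remission is lost (27 of 112 days in the example), assuming that remission resumes at that assessment.

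The effect on the treatment comparison cannot be computed, because use by arm is not given. A reader might infer a bias in a known direction. The documents do not establish one; higher use on placebo would dilute the odds ratio towards 1. A reader might also infer a threat to the trial's main conclusions, but the primary and key secondary endpoints have their own rules. Under SAP 4.2.8.2 this endpoint has a nominal p-value outside the testing hierarchy. Only it and the exploratory variant in SAP 3.4.2.1 are affected.

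**What to change.** In SAP 3.4.2 and 3.4.2.1, replace the relapse rule for restricted medications with: *No time on or after the start of a medication deemed an intercurrent event per Section 3.1.5.2 is counted as time in remission off OCS, up to Week 36.* This brings the endpoint into line with SAP 3.2 and 3.4.3.

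The cost is one sentence and one line of derivation code, with no new data; SAP 3.4.2 already rules out missing or partial start dates for these medications. There is one small downside. Time after a short, completed course of such a drug given for BP would also not be counted, as is already so for the primary endpoint. If the sponsor does want later remission to count, SAP 3.4.2 should say so and give the reason. Either way it should be settled before unblinding.
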